16.1.1. Solicited Adverse Events

Solicited administration site events and solicited systemic events to be summarized are included in Table H. Intensity scales for solicited events (administration site and systemic) are included in Table I and Table J.

Table H: Solicited events

Solicited administration site events	Solicited systemic events
Pain at Injection Site	Fever
Erythema / Redness at Injection Site	Headache
Swelling at Injection Site	Fatigue
	Myalgia
	Arthralgia

Table I: Intensity scales for solicited events – pain, headache, fatigue, myalgia and arthralgia

Event	Intensity grade	Parameter
Pain at administration site	0	None
	1	Mild: Any pain neither interfering with nor preventing normal everyday activities.
	2	Moderate: Painful when limb is moved and interferes with everyday activities.
	3	Severe: Significant pain at rest. Prevents normal everyday activities.
Headache	0	None
	1	Mild: Headache that is easily tolerated
	2	Moderate: Headache that interferes with normal activity
	3	Severe: Headache that prevents normal activity
Fatigue	0	None
	1	Mild: Fatigue that is easily tolerated
	2	Moderate: Fatigue that interferes with normal activity
	3	Severe: Fatigue that prevents normal activity
Myalgia	0	None
	1	Mild: Myalgia that is easily tolerated
	2	Moderate: Myalgia that interferes with normal activity
	3	Severe: Myalgia that prevents normal activity
Arthralgia	0	None
	1	Mild: Arthralgia that is easily tolerated
	2	Moderate: Arthralgia that interferes with normal activity
	3	Severe: Arthralgia that prevents normal activity

Table J: Intensity scales for solicited events – erythema/swelling and fever

	Erythema/swelling	Fever (Temp °C)
0:	≤20 mm	<38.0 °C <100.4 °F
1:	> 20 - ≤50 mm	≥38.0 °C (100.4 °F) - ≤38.5 °C (101.3 °F)
2:	> 50 - ≤100 mm	>38.5 °C (101.3 °F) - ≤39.0 °C (102.2 °F)
3:	>100 mm	>39.0 °C (102.2 °F)

Table K: Solicited events lower level term codes and decodes

Solicited event	Lower level term code	Corresponding Lower level term decode
Pain	10022086	Injection site pain
Erythema	10022061	Injection site erythema
Swelling	10053425	Injection site swelling
Fever	10016558	Fever
Headache	10019211	Headache
Fatigue	10016256	Fatigue
Myalgia	10028411	Myalgia
Arthralgia	10003239	Arthralgia

Solicited events will be summarized and listed as:

- The number and percentage of participants and doses with at least one administration site event (solicited only), with at least one systemic event (solicited only), with any solicited event during 4-day follow-up period and 7-day follow-up period after vaccination, and also events ongoing at the end of the 7 day follow-up period, will be tabulated with exact 95% CI after each dose and overall, by visit. This summary will be repeated by age group.
- The number and percentage of participants, with exact 95% CIs, reporting each solicited event (administration site and/or systemic) will be summarized separately for any grades, Grade 3 and medically attended events during the 4-day follow-up and the 7-day follow-up period (i.e., the day of vaccination and 6 subsequent days), following each dose and overall dose and overall participant. This summary will be repeated by age group.
- The number and percentage of participants, with exact 95% CIs, reporting administration site solicited events (pain, erythema, swelling) will be summarized separately for any grades, Grade 3 and medically attended

events during the 7-day follow-up period (i.e., the day of vaccination and 6 subsequent days) and 4-day follow-up period following each dose and overall and overall participant. This summary will also be repeated by age group.

- The number and percentage of participants, with exact 95% CIs, reporting systemic solicited events (fever, headache, fatigue, myalgia, arthralgia) will be summarized separately for any grades, Grade 3 and medically attended events during the 30-day follow-up period (i.e., the day of vaccination and 29 subsequent days), 7 day follow-up period and 4-day follow-up period following each dose, overall dose, and overall participant. This summary will also be repeated by age group.
- Duration in days of solicited events will be summarized as follows:

The duration of an event with a start and end date will be the difference between the start and end date plus one day, i.e., an event that starts on 03MAR2018 and ends on 12MAR2018, has a duration of 10 days.

For solicited administration site and systemic events (including grade 3):

- The duration of a solicited AE with at least one day Grade > 0 is defined as End date (CEENDY) – Start date (CESTDY) + 1, with Start date defined as the first day with the symptom and End date defined as the last day with the symptom in or beyond the solicited period.
- A missing start date will be imputed with the vaccination date.
- If a solicited event intensity is still Grade > 0 at day 30, then end date will be considered equal to vaccination date + 29 days.
- The number of days with grade 3 solicited symptom will be defined considering each day with a known grading=3, irrespective of whether the days are consecutive.

- For fever, the number and percentage of participants reporting fever by half degree (°C) cumulative increments in applicable systemic event summaries.
- The percentage of participants with each solicited administration site event and solicited systemic event (any grade and Grade 3) will be represented graphically for each group after each dose, during the 4-day and 7-day follow-up period.
- All solicited administration site events will be included in a listing.
- All solicited systemic events will be included in a listing.
- Sensitivity analysis will be performed to present differences in severity/intensity scales between participant and principal investigator assessments for solicited events: erythema, swelling and fever. All summaries and

listings aside from this sensitivity analysis are based on the participant assessments – only the sensitivity outputs will be based on the investigator assessment. This will be summarized separately for the solicited administration site events (erythema and swelling) and for the solicited systemic event (fever). The differences between participant and principal investigator assessments will be included in a listing.

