2.5. Sample size determination

[figure not shown]
The target enrollment will be 1090 participants (545 in the group receiving the RSVPreF3 OA investigational vaccine co-administered with PCV20 [Co-Ad group] and 545 in the Control group where RSVPreF3 OA investigational vaccine and PCV20 are administered in a staggered manner). This allows to obtain at least 980 evaluable participants (490 in the Co-Ad group and 490 in the Control group) for the evaluation of the primary objectives, assuming that 10% of the enrolled participants will not be evaluable.

Participants who withdraw from the study will not be replaced.

Each objective will be evaluated with a nominal type I error of 2.5%.

Table A: Overall power to demonstrate primary objectives: non-inferiority of the immunogenicity of RSVPreF3 OA investigational vaccine when co-administered with pneumococcal vaccine (PCV20) as compared to when administered alone- assuming 490 evaluable participants in each group Groups

Endpoint	Standard deviation of log10 concentration	Reference ratio	Non inferiority margin	Type II error	Power
PCV Non-inferiority* (1-sided test with alpha=2.5%)					
GMTs Opsonophagocytic (OP) antibody (Ab)					
3	0.572	1.05	2	<0.01%	>99.99%
7F	0.733	1.05	2	0.01%	99.99%
19A	0.771	1.05	2	0.01%	99.99%
5	0.782	1.05	2	0.02%	99.98%
1	0.789	1.05	2	0.02%	99.98%
14	0.792	1.05	2	0.02%	99.98%
8	0.797	1.05	2	0.03%	99.97%
33F	0.797	1.05	2	0.03%	99.97%
9V	0.825	1.05	2	0.05%	99.95%
10A	0.839	1.05	2	0.06%	99.94%
11A	0.843	1.05	2	0.07%	99.93%
19F	0.845	1.05	2	0.07%	99.93%

6B	0.882	1.05	2	0.14%	99.86%
4	0.902	1.05	2	0.20%	99.80%
18C	0.910	1.05	2	0.22%	99.78%
6A	0.927	1.05	2	0.29%	99.71%
12F	0.943	1.05	2	0.37%	99.63%
22F	0.966	1.05	2	0.51%	99.49%
15B	1.088	1.05	2	1.96%	98.04%
23F	1.096	1.05	2	2.10%	97.90%
Global Type II error to show non-inferiority				~6.2%	
Global power for PCV					~93.8%
RSV-A Non-inferiority* (1-sided test with alpha = 2.5%)					
GMTs	RSV-A	0.45	1.05	1.5	0.04%
neutralization antibody					99.96%
RSV-B Non-inferiority* (1-sided test with alpha = 2.5%)					
GMTs	RSV-B	0.45	1.05	1.5	0.04%
neutralization antibody					99.96%
Global Power for the study				~6.28	~93.7

Abbreviations: Ab=antibody; GMT=geometric mean titer; OA=older adult; OP=opsonophagocytic; PCV=pneumococcal vaccine; RSV=respiratory syncytial virus.

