3. STUDY DESIGN

3.1. General Description

This is a phase III, open-label, randomized, controlled, multi-country study in healthy older adults of ≥ 60 YOA with two parallel groups. Participants will be randomly assigned to 2 study groups at Visit 1 (Day 1):

- Co-administration (Co-Ad) group: Study intervention administration of RSVPreF3 OA investigational vaccine and PCV20 vaccine co-administered on Visit 1 (Day 1)
- Control group: Study intervention administrations of PCV20 vaccine on Visit 1 (Day 1) and RSVPreF3 OA investigational vaccine on Visit 2 (Day 31).

Figure A: Study Schema

- AE=Adverse Event; Co-Ad group=Co-Administration group; D=Day; N=Number of participants; PCV=20-valent pneumococcal conjugate vaccine; pIMD=potential Immune-Mediated Disease; RSV=RSVPreF3 OA; SAE=Serious Adverse Event.
- Healthy older adults ≥ 60 YOA will be enrolled in this study according to the inclusion and exclusion criteria (see protocol Section 5.0). Approximately 1090 participants will be randomly assigned to the 2 study intervention groups in a 1:1 ratio prior to intervention to provide approximately 545 enrolled participants in each study intervention group.

The randomization algorithm will use a minimization procedure accounting for age (60-69, 70-79, or ≥ 80 years) and center. Minimization factors will have equal weight in the minimization algorithm. Participants will be enrolled in 3 age categories with a balance between males and females. It is intended to enroll:

- Approximately 40% of participants 60 to 69 YOA, approximately 30% of participants 70 to 79 YOA, and approximately 10% of participants ≥ 80 YOA. The remaining 20% will be distributed freely across the 3 age categories.
- Approximately 40% of participants from each sex. The remaining 20% can be distributed freely across the 2 sexes.

Table A: Study Groups

Study groups	Number of participants	Age (min)	Study interventions
Co-Ad	545	≥ 60 years	RSVPreF3 OA and PCV20 co-administered
Control	545	≥ 60 years	RSVPreF3 OA and PCV20 administered separately

The total duration of the study participation differs for the 2 study intervention groups:

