6.5. Statistical Tests

The default significant level will be (5%), CIs will be 95% and all tests will be two-sided, unless otherwise specified in the description of the analyses.

95% CI for proportion will be based on exact Clopper-Pearson CI [18].

95% CI for group difference in proportion will be based on Miettinen and Nurminen CI [18].

The group adjusted GMT ratio will be based on a back transformation of group contrast in an ANCOVA model applied to the logarithm-transformed titers.

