13. MEDICATIONS

The number and percentage of participants and doses using concomitant medication (any medication, any antipyretic and any antipyretic taken prophylactically, respectively) during the 7-day follow-up period (i.e., on the day of vaccination and 6 subsequent days), during the 30-day follow-up period (i.e., on the day of vaccination and 29

subsequent days) and during the 6-month follow-up period (i.e., up to EoS) will be summarized by study intervention group for each study intervention administration and overall will be summarized with exact 95% CIs for the ES. See [APPENDIX 2](#) for handling of partial dates for medications, in the case where it is not possible to define a medication as prior or concomitant, the medication will be classified by the worst case; i.e., concomitant.

- ‘Prior’ medications are medications which started prior to the dose of study intervention.
- ‘Concomitant’ medications are medications which started on or after the day of the administration of study intervention.

Further details are in Section 6.7 of the Protocol. Concomitant medications that start within the 7-days follow-up period and within the 30-days follow-up period post each dose will be presented in table summaries (Any, antipyretic action) for the ES and in listings for all medications. This summary will also be repeated for any concomitant medications that start from day of administration up to End of Study.

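### Overall-dose safety rows get exact binomial CIs that treat one participant's two doses as independent, and the SAP does not define a dose for Co-Ad systemic, any-solicited and medication rows

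*SAP*

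**What the plan says.** SAP 16.1.1 opens its list of solicited-event summaries with "The number and percentage of participants and doses with at least one administration site event (solicited only), with at least one systemic event" or any solicited event; these "will be tabulated with exact 95% CI after each dose and overall, by visit". A later item in the same section, on systemic events, asks for results over the "7 day follow-up period and 4-day follow-up period following each dose, overall dose, and overall participant". SAP 13 plans "The number and percentage of participants and doses using concomitant medication", per administration and overall, with exact 95% CIs. SAP 16.1.3 also lists an overall-dose row with exact CIs for combined solicited and unsolicited events.

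SAP 6.5 sets one method: "95% CI for proportion will be based on exact Clopper-Pearson CI". Neither document provides an adjustment for repeated doses in one person.

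Under SAP 3.1 both groups receive two vaccines. Co-Ad receives both on Day 1; Control receives PCV20 on Day 1 and RSVPreF3 OA on Day 31. Protocol Table 5 puts the two Co-Ad injections in opposite arms.

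**The concern.** A Clopper-Pearson interval is exact only when the trials are independent. A row that pools doses has up to two records from each participant, and people who react to one injection may well be likelier to react to another. If so, the interval is narrower than the data justify, yet it is labelled exact.

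There is also a definitional gap. A Co-Ad participant has two injection sites, so a local reaction can be assigned to an injection. A fever, a headache or a concomitant drug in the shared follow-up window cannot. The SAP does not say whether co-administration then counts as one dose or two, so the Co-Ad denominator for those rows rests on a programming choice. The question does not arise in Control.

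At stake is the description of reactogenicity when the vaccines are given together or apart, which is a secondary objective (SAP 2.2).

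**Working it through.** **Inputs.** From SAP 2.5: 490 evaluable participants per group and 10% not evaluable. From SAP 3.1: two vaccines per participant. Assumed, because the documents give neither: event rates of 5% to 50% where the two doses have equal rates, the unequal pairs shown in step 4, and a within-person correlation ρ from 0 to 1.

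**1. The plan's own figure.** 490 / (1 − 0.10) = 544.4, rounded up to 545 per group, as stated. A pooled row can then hold up to 2 × 545 = 1,090 doses per group. The SAP states neither a dose denominator nor a CI width.

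**2. Formulas.** For x events in n records, the Clopper-Pearson limits are the 2.5% quantile of Beta(x, n − x + 1) and the 97.5% quantile of Beta(x + 1, n − x). For N participants with two doses at rates p1 and p2, and mean rate p:

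- true variance = [p1(1 − p1) + p2(1 − p2) + 2ρ√(p1(1 − p1)p2(1 − p2))] / (4N)
- variance assumed by the binomial = p(1 − p) / (2N)
- design effect = the first divided by the second, which is 1 + ρ when p1 = p2.

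**3. Equal rates.** Simulated coverage of the nominal 95% interval for 545 pairs (400,000 replicates per scenario, rates 5% to 50%):

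| ρ | Design effect | Width should be multiplied by √(1 + ρ) | Coverage |
|---|---|---|---|
| 0 | 1.0 | 1.00 | 95.2-95.7% |
| 0.1 | 1.1 | 1.05 | 93.9-94.6% |
| 0.3 | 1.3 | 1.14 | 91.7-92.3% |
| 0.5 | 1.5 | 1.22 | 89.3-90.1% |
| 1.0 | 2.0 | 1.41 | 83.0-84.6% |

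The last line is pure duplication, where one result is entered for both doses. For example, 328/1,090 gives 27.4-32.9% (width 5.5 points), while the same people counted once, 164/545, give 26.3-34.1% (7.9 points), which is 1.42 times as wide.

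**4. Unequal rates.** With p1 = 60%, p2 = 30% and ρ = 0.1, p is 45%. Leaving out the common factor 1/N, the binomial variance is 0.45 × 0.55 / 2 = 0.1238. The true variance is (0.24 + 0.21 + 2 × 0.1 × √(0.24 × 0.21)) / 4 = 0.1237. The design effect is 1.00.

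| Rates | ρ | Design effect | Coverage |
|---|---|---|---|
| 60% / 30% | 0 | 0.91 | about 96.5% |
| 60% / 30% | 0.1 | 1.00 | about 95.6% |
| 60% / 30% | 0.3 | 1.18 | about 93.6% |
| 70% / 30% | 0 | 0.84 | about 96.8% |
| 70% / 30% | 0.2 | 1.01 | about 95.0% |
| 70% / 30% | 0.3 | 1.09 | about 94.1% |

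**5. Which rows.** The Control overall-dose rows hold two records per fully vaccinated person under any reading. Co-Ad administration-site rows do too, because there are two injection sites. Co-Ad systemic, any-solicited and medication rows do so only if co-administration counts as two doses. If it counts as one, n is 545, the dose and participant rows coincide, and the interval is correct. Per-dose rows and overall-participant rows have one record per person and are valid throughout.

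**The case against.** The strongest reply is that the documents lean towards treating co-administration as one dosing occasion. The SAP version history says that systemic solicited events are now summarized by dosing visit. The first summary in SAP 16.1.1 is produced by visit. Protocol Table 8 labels the Co-Ad Day 31 sample as following dose 1. SAP 16.1.1.1 reports eDiary compliance by dose with the number of participants as denominator. In addition, SAP 8 leaves table content to templates that were not available here and may define the denominator.

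Much of this stands. A reader might infer that every Co-Ad systemic event is entered against two doses, so that coverage falls to 83-85%, or is entered once over 1,090 doses, so that the percentage is halved. The documents state neither rule, and on the one-occasion reading both effects disappear. What remains is that the SAP text does not settle the matter: the estimand table in SAP 2.4 refers to each vaccine for systemic as well as local events, and SAP 16.1.1 still lists an overall-dose row for systemic events.

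A second reply is that the consequence is small. This also stands. The endpoints are percentages of participants, participant-level rows with exact CIs are planned alongside, and SAP 16 rules out statistical comparison of the groups on safety. It does not justify calling an interval exact when its independence assumption fails.

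**Conclusion.** Wrong as written, but minor. The interval method for pooled-dose rows is invalid for Control and for Co-Ad administration-site events, and its validity is undetermined for Co-Ad systemic, any-solicited and medication rows.

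The size depends on assumed values. With equal rates for the two doses, the coverage loss is about one point or less at ρ = 0.1, about three points at 0.3 and about five points at 0.5. The larger loss, to 83-85%, needs full duplication, which the documents do not establish.

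It would be tempting to say that all overall-dose intervals are too narrow. The documents do not support that. It requires a clearly positive within-person correlation, for which they give no figure, and in Control the pooled doses are two different vaccines whose rates may differ enough to offset weak correlation. Mis-calibrated is the accurate word. No hypothesis test, alpha level, sample size or participant-level endpoint is affected.

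**What to change.** In SAP 16.1.1, 16.1.3 and 13:

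1. On any overall-dose row that is kept, give the percentage without an exact CI, or with a participant-clustered (robust) CI.
2. State that for systemic, any-solicited and medication summaries the unit is the vaccination visit: one per Co-Ad participant and up to two per Control participant. This agrees with the version-history entry on dosing visits. Pooled Control visits are still paired within person, so item 1 applies to them as well.
3. Keep Clopper-Pearson for per-dose and per-participant rows, and say so in SAP 6.5.

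The cost is SAP wording and a small programming change. The downside is that intervals in a few descriptive rows will generally be wider, or will be omitted.

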16.1.1.1. ENDPOINT LEVEL COMPLIANCE

The study protocol defines a 7-day solicited AE follow-up period.

In terms of compliance for each of Days 1-7, the number/percentage of completed eDiaries will be summarized by study group and by dose, using a frequency table. The denominator for each day will be the number of expected completed eDiaries (i.e., the number of participants).

For compliance of each day beyond Day 7, and for each solicited symptom, the number/percentage of completed eDiaries will be summarized by study group and by dose, using a frequency table. In this summary, the denominator for each symptom will be the number of expected completed diaries (i.e., the number of participants with the symptom on the previous days) and the numerator will be the number of participants with eDiaries completed among the participants contributing to the denominator.

16.1.2. Unsolicited Adverse Events

All unsolicited adverse events summaries will be reported by MedDRA SOC, HLT and PT.

The verbatim reports of unsolicited AEs will be reviewed by a physician and the signs and symptoms will be coded according to the MedDRA Dictionary for Adverse Reaction Terminology. Every verbatim term will be matched with the appropriate Preferred Term. The above analysis by dose will also be performed.

Unsolicited events will be summarized and listed as:

- The number and percentage of participants with any unsolicited AEs during the 30-day follow-up period (i.e., the day of vaccination and 29 subsequent days) with its exact 95% CI will be tabulated by group and by MedDRA SOC, HLT and PT. This summary will be repeated by age group.
 - This summary will be repeated for:
 - Grade 3 unsolicited AEs
 - Considered Causally related by investigator unsolicited AEs
 - Grade 3 considered causally related by investigator unsolicited AEs
 - Unsolicited AEs resulting in a medically attended visit

The above analysis by dose will also be performed.

- The number and percentage of participants with any non-serious unsolicited AEs during the 30-day follow-up period (i.e., the day of vaccination and 29 subsequent days) with its exact 95% CI will be tabulated by group and by MedDRA SOC, HLT and PT, following each dose.
 - This summary will be repeated for:
 - Grade 3 non-serious AEs (this summary will be repeated by age group)
 - Considered Causally related by investigator non-serious unsolicited AEs
 - Considered Causally related by investigator, Grade 3 non-serious unsolicited AEs
 - Non-serious unsolicited AEs resulting in a medically attended visit
- The number and percentage of participants, with exact 95% CIs, with any unsolicited AEs with onset within 30-minutes of any dose will be tabulated by group and by MedDRA SOC, HLT and PT, following each dose. This summary will be repeated for Grade 3 only unsolicited AEs.
- The number and percentage of participants, with exact 95% CIs, by each AE category (including unsolicited AEs within 30 days of any dose, Grade 3/related/Grade 3 related/medically attended unsolicited AEs within 30 days of any dose, non-serious AEs, serious AEs, pIMDs, fatal serious AEs) will be tabulated by group.
- All of the summaries for unsolicited AEs during the 30-day follow-up period and non-serious unsolicited AEs during the 30-day follow-up period will be repeated by visit.
- A list of unsolicited AEs leading to study discontinuation or vaccine discontinuation (for Control group only) from dose 1 up to the study end will be tabulated by study intervention group (Co-Ad and Control) for each study intervention administration (RSVPreF3 OA, PCV20), by MedDRA, SOC, HLT and PT.
- All unsolicited AEs will be included in a listing.

